10.6. Appendix 6: Protocol Amendment change history

The Protocol Amendment Summary of Changes Table for the current amendment is located directly before the Table of Contents.

**VERSION HISTORY**

SAP Version	Approval Date	Protocol Version (Date) on which SAP is Based	Change	Rationale
SAP	25 Aug 2023	13 May 2022	Not Applicable	Original version

## 1. INTRODUCTION

The purpose of this SAP is to describe the planned analyses to be included in the clinical study report (CSR) for study ROTA-097 (212692). Details of the planned analyses are provided.

### 1.1. Objectives, Estimands and Endpoints

[figure not shown]
Objectives	Endpoints**

 
• To demonstrate the immunological non-inferiority of Rotarix PCV-free as compared to Rotarix in terms of seroconversion rates 1 month post Dose 2. 
 
– Non-inferiority will be demonstrated if the lower limit of the two-sided asymptotic standardized 95% CI for the difference in seroconversion rate between the Rotarix PCV-free and Rotarix is greater than or equal to -10%.
 
 
 
• To demonstrate the non-inferiority of the Rotarix PCV-free as compared to Rotarix in terms of serum anti-RV IgA Ab concentrations 1 month post Dose 2. 
 
– Non-inferiority will be demonstrated if the lower limit of the two-sided 95% CI for the ratio of anti-RV IgA Ab geometric mean concentration (GMC) 1 month post Dose 2 between the Rotarix PCV-free and Rotarix is greater than or equal to 0.67.
 
 
 
	
Evaluation of immunogenicity in terms of anti-RV antibody concentrations.
 
 
• Anti-RV IgA Ab seroconversion rate* 1 month post Dose 2 in the Rotarix PCV-free and Rotarix groups.
 
• Serum anti-RV IgA Ab concentrations expressed as GMCs 1 month post Dose 2 in the Rotarix PCV-free and Rotarix groups.
 
 
*Seroconversion rate is defined as the percentage of participants who were initially seronegative (i.e., with anti-RV IgA Ab concentration < 20 U/mL prior the first dose of Rotarix) and developed anti-RV IgA Ab concentration ≥ 20 U/mL at Visit 3 (1 month post Dose 2).


 
• To assess the immunological non-inferiority of Rotarix PCV-free as compared to Rotarix in terms of percentage of participants with anti-RV IgA antibody concentrations ≥ 90 U/mL 1 month post Dose 2. 
 
– Non-inferiority will be demonstrated if the lower limit of the two-sided asymptotic standardized 95% CI for the difference in the percentage between the Rotarix PCV-free and Rotarix is greater than or equal to -10%.
 
 
 
	
Evaluation of immunogenicity in terms of anti-RV antibody concentrations.
 
 
• Percentage of participants with serum anti-RV IgA antibody concentrations ≥ 90 U/mL 1 month post Dose 2 in Rotarix PCV-free and Rotarix groups.
 

 
• To evaluate the reactogenicity of Rotarix PCV-free and Rotarix in terms of solicited systemic events.
 
• To assess the safety of Rotarix PCV-free and Rotarix in terms of unsolicited AEs and serious adverse events (SAEs).
 
	
 
• Solicited AEs 
 
– For each solicited systemic event, percentage of participants reporting the occurrence of the event within 14 days (Day 1- Day 14) after each study intervention administration.
 
 
 
• Unsolicited AEs 
 
– Percentage of participants reporting the occurrence of unsolicited AEs within 31 days (Day 1- Day 31) after each study intervention administration, according to the
 
 
 

Objectives	Endpoints**
	
Medical Dictionary for Regulatory Activities (MedDRA) classification.
 
 
SAEs 
 
Percentage of participants reporting the occurrence of SAEs from Dose 1 of the study intervention up to study end.
 
 
 

Ab = Antibody; AE = Adverse event; CI = Confidence Interval; IgA = Immunoglobulin A; GMC = Geometric mean Ab concentration; MedDRA = Medical Dictionary for Regulatory Activities; PCV = Porcine circovirus; PCV-free = No detection of PCV-1 and PCV-2 according to the limit of detection of the tests used; SAE = Serious adverse event; RV = Rotavirus; U = Unit; mL = milliliter

\*\* complementary details on estimand including impact of intercurrent events on the analysis is available in Sections 3 and 4.

## 1.2. Study Design

N = number of participants; AE = adverse event; SAE = serious adverse event; EoS: end of study; ESFU: extended safety follow-up; HRV: Human Rotavirus; PCV-free = No detection of PCV-1 and PCV-2 according to the limit of detection of the tests used.

\* An ESFU contact (by telephone call or any convenient procedure) 6 months post Dose 2.

+ Refer to Section 4.7 "Interim Analyses" for detailed information about sequence of analyses.

### Overview of Study Design and Key Features

Design Features	
 
• Experimental design: Phase III, self-contained, observer-blind, randomized, multicenter study with 2 parallel groups.
 
• Duration of the study: The total duration of the study, per participant, will be approximately 7 months including the 6 months of extended safety follow-up (ESFU) period after the last dose of study intervention.
 
• Primary completion date: Visit 3 (Month 2).
 
• Control: Active control, GSK's human rotavirus (HRV) liquid vaccine (Rotarix).
 
• Blinding: Observer-blind.
 
• Data collection: Standardized electronic Case Report Form (eCRF). Solicited systemic events will be collected using a diary card.
 
• Study groups: Refer to Figure 1 and Table 1 for an overview of the study groups.
 
						

**Table 1** Study groups, intervention and blinding foreseen in the study

Study Groups	Number of participants	Age (Min-Max)	Study intervention (s)	Blinding		
				Visit 1→Visit 2 (Observer-blind)	Visit 2→Visit 3 (Observer-blind)	Visit 3→ESFU contact (Observer-blind)*
HRV	1000	6 – 16 weeks	HRV RIX4414 live attenuated $\geq 10^{6.0} \text{CCID}_5$	X	X	X
HRV PCV-free	1000	6 – 16 weeks	HRV PCV-free RIX4414 live attenuated $\geq 10^{6.0} \text{CCID}_5$	X	X	X

\*Observer-blind except for a limited number of GSK personnel. For unblinding after Visit 3, refer to Section [4.7](#).

ESFU: extended safety follow-up

Overview of Study Design and Key Features			
Study intervention	Study intervention name	HRV ( Rotarix )	HRV PCV-free ( Rotarix PCV-free )
	Presentation	CC1	
	Study interventions formulation	Human Rotavirus, Live Attenuated, RIX4414 strain ( $\geq 10^{6.0}$ CCID 50 ); Sucrose (1.073 g); Di-sodium adipate; DMEM; Sterile water q.s. 1.5 mL	Human Rotavirus, Live Attenuated, RIX4414 strain ( $\geq 10^{6.0}$ CCID 50 ); Sucrose (1.073 g); Di-sodium adipate; DMEM; Sterile water q.s. 1.5 mL
	Type	Control	Study
	Route of administration	Oral use	Oral use
	Number of doses to be administered	2	2
	Volume to be administered	1.5 mL	1.5 mL
	Packaging, labeling and TM	Refer to SPM for more details	Refer to SPM for more details
	Manufacturer	GSK	GSK
	mL: milliliter; qs: quantum satis (the amount which is enough); SPM: study procedures manual		
Study intervention Assignment	
Participants will be randomly assigned (1:1) to the 2 study groups (HRV and HRV PCV-free).
 
The numbering of HRV vaccine supplies will be performed at GSK, using a block scheme randomization in MATerial EXcellence, a program developed by GSK. Entire blocks will be shipped to the study centers/warehouse(s).
 
To allow GSK to take advantage of greater rates of recruitment than anticipated at individual centers in this multicenter study and to thus reduce the overall study recruitment period, an over-randomization of supplies will be prepared.
		
Interim Analysis	
No interim analysis is planned.
 
The final analysis addressing confirmatory objectives will be conducted once anti-RV IgA ELISA testing at Visit 3 (1 month after Dose 2) is completed and all the immunogenicity data are available. This final analysis will include immunogenicity and reactogenicity data up to Visit 3 and a CSR will be written.
 
An EoS analysis with all data including the data obtained during ESFU period will be performed and an integrated CSR will be written and made available to the investigators and submitted to regulatory authorities as appropriate.
		

## 2. STATISTICAL HYPOTHESES

Objective ranking	Null hypothesis

Primary
 
 
1. To demonstrate the immunological non-inferiority of Rotarix PCV-free as compared to Rotarix in terms of seroconversion rates 1 month post Dose 2.           
 
– Non-inferiority will be demonstrated if the lower limit of the two-sided asymptotic standardized 95% CI for the difference in seroconversion rate between the Rotarix PCV-free and Rotarix is greater than or equal to -10%.
 
 
 
2. To demonstrate the non-inferiority of the Rotarix PCV-free as compared to Rotarix in terms of serum anti-RV IgA Ab concentrations 1 month post Dose 2.           
 
– Non-inferiority will be demonstrated if the lower limit of the two-sided 95% CI for the ratio of anti-RV IgA Ab geometric mean concentration (GMC) 1 month post Dose 2 between the Rotarix PCV-free and Rotarix is greater than or equal to 0.67.
 
 
 
	
 
• The difference in seroconversion rate between the Rotarix PCV-free and (minus) Rotarix is < -10%.
 
• The group ratio of anti-RV IgA Ab GMC 1 month post Dose 2 between the Rotarix PCV-free and (over) Rotarix is < 0.67.
 

Secondary
 
 
3. To assess the immunological non-inferiority of Rotarix PCV-free as compared to Rotarix in terms of percentage of subjects with anti-RV IgA antibody concentrations <math>\geq 90</math> U/mL 1 month post Dose 2.           
 
– Non-inferiority will be demonstrated if the lower limit of the two-sided asymptotic standardized 95% CI for the difference in the percentage between the Rotarix PCV-free and Rotarix is greater than or equal to -10%.
 
 
 
	
The difference in the percentage of participants with serum anti-RV IgA antibody concentrations <math>\geq 90</math> U/mL 1 month post Dose 2 between Rotarix PCV-free and (minus) Rotarix groups is < -10%.

### 2.1. Multiplicity Adjustment

To control the type 1 error for the primary objectives and first secondary objective assessment, a hierarchical procedure will be used based on the ranking presented in Section 2. Namely an objective will be reached if its null hypothesis is rejected, and the null hypotheses of the previous objectives were rejected.

Refer to Section 5 “Sample Size Determination” for additional details.

### 3. ANALYSIS SETS

**Table 2 Population for analyses**

Analysis Set	Definition / Criteria	Analyses Evaluated
Enrolled	
 
• All participants who entered the study (who were randomized or received study intervention or underwent a post-screening procedure)
 
• NOTE: screening failures (who never passed screening even if rescreened) and participants screened but never enrolled into the study (Met eligibility but not needed) are excluded from the Enrolled Analysis set as they did not enter the study.
 
	
 
• Study Population
 

Exposed	
 
• All participants who received at least one dose of study intervention.
 
• Participants will be analysed according to the study intervention administered at dose 1.
 
	
 
• Safety
 

Per-Protocol (PP)	
All eligible participants from the exposed set who meet the following requirements:
 
 
• Who received the study interventions according to their random assignment and the expected study intervention administration schedule ([28-48] days between first and second intervention). Note that in case regurgitation or vomiting occurs within 30 minutes after study intervention administration and impairs up-take of the intervention, a single replacement dose should be used for the participant to be part of the PPS.
 
• Who were not unblinded
 
• Who did not receive a vaccine not specified or forbidden by the protocol up to visit 3 blood sampling
 
• Who did not receive medication forbidden by the protocol up to Visit 3 blood sampling.
 
• Who had anti-RV concentration below 20 U/mL before study intervention.
 
• Who complied with the blood sampling schedule for Visit 3 ([28-48] days between second intervention at Visit 2 and blood sample at Visit 3).
 
• Who had no concomitant infection* up to Visit 3 blood sample, which may influence the immune system.
 
• Participants will be analysed according to the intervention they received at dose 1.
 
	
 
• The PP Set will be used for the immunogenicity analyses. If, in any study intervention group, the percentage of vaccinated participants with serological results excluded from the PP Set for analysis of immunogenicity is 5% or more, a second analysis based on the Exposed Set will be performed to complement the PP Set analysis.
 

GCP = Good Clinical Practice; LAR = Legally Acceptable Representative

\* RV gastroenteritis, immunosuppressive or immunodeficient conditions identified before Visit 3.

## 4. STATISTICAL ANALYSES

### 4.1. General Considerations

#### 4.1.1. Immunogenicity

- Anti-RV IgA Ab concentrations below the assay cut-off will be given an arbitrary value of half the assay cut-off for the purpose of GMC calculation.
- The GMC calculations will be performed by taking the anti-log of the mean of the log concentration transformations.
- A participant is considered seronegative when the Anti-RV IgA Ab concentration is < 20 U/mL and seropositive when  $\geq 20$  U/mL.
- Seroconversion is defined as the percentage of participants who were initially seronegative (i.e., prior the first dose of *Rotarix*) and developed anti-RV IgA Ab concentration  $\geq 20$  U/mL at Visit 3 (1 month post Dose 2).
- For a given participant and a given immunogenicity measurement time point, missing or non-evaluable measurements will not be replaced.

#### 4.1.2. Reactogenicity

Participants without events (solicited/unsolicited AEs or concomitant medications) reported will be treated as participants without the events (solicited/unsolicited AEs or concomitant medications, respectively).

Refer to Section 6.2.4.2 for the intensity grading of solicited AEs.

### 4.2. Primary Endpoint(s) Analyses

Analyses on the immunogenicity endpoints will be conducted primarily on the Per Protocol Set.

#### 4.2.1. Within groups assessment

The following calculations will be performed.

For each group, at Visit 1 and Visit 3 time point,

- Seropositivity (at Visit 1 and Visit 3) and Seroconversion rates (at Visit 3) and their exact 95% confidence interval (CI) will be computed using the method of Clopper and Pearson [[Clopper](#), 1934],
- GMCs and their exact 95% CIs will be computed,

#### **4.2.2. Between groups assessment**

- The asymptotic standardized 95% CI for the difference in seroconversion rate at Visit 3 between *Rotarix* PCV-free minus *Rotarix* will be computed using the method of Miettinen and Nurminen [Miettinen, 1985].
- The 95% CI for the ratio of anti-RV IgA Ab GMCs at Visit 3 between *Rotarix* PCV-free over *Rotarix* will be computed.

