6.3.3. Intervention allocation to the participant

The system's randomization algorithm will use a minimization procedure accounting for center and the study as a whole as minimization factors.

Upon providing the participant identification number, the randomization system will determine the study group and will provide the intervention number to be used for the first study intervention administration. The intervention number(s) to be used for subsequent dose administration(s) will be provided by the same automated Internet-based system.

When source data base for internet randomization (SBIR) is not available, please refer to the SBIR user guide or SPM for specific instructions.

Refer to the SPM for additional information relative to the intervention number allocation.

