#### **4.2.3. Sensitivity analyses**

If more than 5% of the ES participants with immunogenicity results after study intervention are excluded from the PPS, the confirmatory analyses (refer to Section 2) will be repeated on the ES.

Within groups assessment for the PPS will be repeated by sex and study sites.

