#### **4.3.2. Between group assessment**

- The asymptotic standardized 95% CI for the difference in the percentage of participants with anti-RV IgA antibody concentrations  $\geq 90$  U/mL at Visit 3 between *Rotarix* PCV-free minus *Rotarix* will be computed.

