## 4.8. Changes to Protocol Defined Analyses

There were no changes or deviations to the originally planned statistical analysis specified in the protocol (Dated: 13 May 2022).

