# 5. SAMPLE SIZE DETERMINATION

A maximum of 2000 participants (1000 per arm) will be randomized such that approximately 1500 evaluable participants complete the study, considering that 25% of the participants will not be evaluable for the analysis of the primary endpoint leading to 750 evaluable participants per arm.

To control the type 1 error for the primary objectives and first secondary objective a hierarchical procedure will be used. Namely the primary objective on ratio of anti-RV IgA Ab GMCs will be conclusive if the success criterion is reached and the first primary objective is met. The first secondary objective will be conclusive if the success criterion is reached and the 2 primary objectives are met.

The sample size provides at least 90% power to reach the first primary endpoint (see [Table 3](#)) and at 80.7% power to reach the second primary endpoint. 80.7% is a very conservative power estimate and is obtained as 100% minus the sum of type II errors for the 2 primary objectives, see [Table 3](#) and [Table 4](#). Using the same approach, the power to meet the first secondary objectives will be at least 67% power.

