### 5.1.2. Power for non-inferiority in GMC

The power presented in [Table 4](#) is based on PASS 2019 (one-sided non-inferiority test for 2 independent means, under the alternative of equal variance & alpha=2.5%).

**Table 4 Probability that the lower limit of the 95% CI around the anti-RV IgA Ab GMC ratio (*Rotarix* PCV-free / *Rotarix*), 1 month after Dose 2 of *Rotarix*, is  $\geq 0.67$**

Endpoint	True group GMC ratio	Standard deviation [ $\text{Log}_{10}$ (titer)]	N evaluable (each Rotarix group)	Power	Alpha
Anti-RV IgA Ab concentration	1	0.797*	750	99.0%	0.025
Anti-RV IgA Ab concentration	0.91	0.797*	750	90.7%	0.025

\* = Reference from Rota-075

N = number of participants

### 5.1.3. Power for non-inferiority in the percentage of participants with serum anti-RV IgA antibody concentrations greater or equal to 90 U/mL 1 month post Dose 2

The power presented in [Table 5](#) is based on PASS 2019 (one-sided Non-Inferiority Tests for the Difference Between Two Proportions), under the alternative hypothesis of a 45.7% and 43.5% percentage for *Rotarix* and *Rotarix* PCV-free, respectively, [Miettinen](#) and [Nurminen](#)'s Likelihood Score Test of the Difference).

**Table 5 Probability that the lower limit of the 95% CI around group difference in the percentage of participants with serum anti-RV IgA antibody concentrations greater or equal to 90 U/mL (*Rotarix* PCV-free minus *Rotarix*), 1 month after Dose 2 of *Rotarix*, is  $\geq -10\%$**

Expected rate ( Rotarix / Rotarix PCV-free)	N evaluable (each Rotarix group)	Power	Alpha
45.7%* / 43.5%	750	86.2%	0.025

\* = Reference from Rota-075

N = number of participants

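### Allocation is minimised by centre, but no confirmatory between-group interval is stated to use centre; if centres differ in IgA response, a small and nearly free gain in power is given up.

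*SAP*

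**What the plan says.** **Allocation.** Protocol 6.3.3 says the "randomization algorithm will use a minimization procedure accounting for center and the study as a whole as minimization factors". Centre is therefore a design factor. The SAP's own account of assignment (section 1.2) does not mention this.

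**Confirmatory intervals.**
- Seroconversion, SAP 4.2.2: "The asymptotic standardized 95% CI for the difference in seroconversion rate at Visit 3 between" the two vaccines, by Miettinen and Nurminen. No stratification is mentioned.
- GMC ratio, SAP 4.2.2: "The 95% CI for the ratio of anti-RV IgA Ab GMCs at Visit 3 between" the two vaccines. No method or model is named.
- ≥90 U/mL, SAP 4.3.2: "The asymptotic standardized 95% CI for the difference in the percentage of participants with anti-RV IgA antibody concentrations" at or above that threshold. Centre is not mentioned.

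Protocol 9.4.3.2 lists the same three intervals and is equally silent on centre.

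**Use of site.** In the immunogenicity analysis, site appears only in SAP 4.2.3 and 4.3.3: "Within groups assessment for the PPS will be repeated by sex and study sites". Those tables do not feed any non-inferiority decision.

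**Power basis.** The calculations also leave centre out. For the GMC ratio, SAP 5.1.2 describes a "one-sided non-inferiority test for 2 independent means, under the alternative of equal variance & alpha=2.5"%.

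**The concern.** Balancing the arms within centre removes between-centre variation from the true error of the group difference. An interval that ignores centre still counts that variation in its standard error. If centres differ in IgA response, the interval is wider than it needs to be and its lower limit sits too low.

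All three decisions in the hierarchy rest on such lower limits. The error is on the safe side for a non-inferiority claim, so what is at stake is power. That matters most for the third objective, which can succeed only after the first two and for which SAP 5 claims at least 67%.

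**Working it through.** **Inputs from the documents** (Protocol 9.2; SAP 2 and 5):
- 750 evaluable per arm, one-sided alpha 0.025.
- Seroconversion 70% against 67.8%, margin −10 points.
- GMC: SD of log10 concentration 0.797, true ratio 0.91, margin 0.67.
- ≥90 U/mL: 45.7% against 43.5%, margin −10 points.
- 25% not evaluable.

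**Assumption.** R is the share of outcome variance due to centre. The documents give neither R nor the number of centres, so R is set to 0, 2, 5 and 10%.

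**Step 1. Reproduce the stated power, ignoring centre.** Let d be the distance from the margin in standard errors; power = Φ(d − 1.96).
- Seroconversion: d = 0.078/√[(0.70×0.30 + 0.678×0.322)/750] = 3.264, power 90.4% (stated 90%).
- GMC: d = log10(0.91/0.67)/(0.797×√(2/750)) = 3.231, power 89.8% (stated 90.7%). With the margin taken as 1/1.5, d = 3.283 and power is 90.7%.
- ≥90 U/mL: d = 0.078/√[(0.457×0.543 + 0.435×0.565)/750] = 3.039, power 86.0% (stated 86.2%; the score-test variance gives 86.2%).
- Hierarchical bounds: 100 − 10 − 9.3 = 80.7%, and 100 − 10 − 9.3 − 13.8 = 66.9%, as stated.

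**Step 2. Bring in centre, with exact balance within centre.** The true variance of the difference shrinks by (1 − R). The adjusted interval uses the smaller variance; the unadjusted one keeps the full variance.
- Adjusted power = Φ(d/√(1 − R) − 1.96)
- Unadjusted power = Φ((d − 1.96)/√(1 − R))
- Unadjusted one-sided error = 1 − Φ(1.96/√(1 − R))

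Power is shown as unadjusted → adjusted.

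| R | Seroconversion, % | GMC, ratio 0.91, % | ≥90 U/mL, % | Unadjusted error, % |
|---|---|---|---|---|
| 0% | 90.4 → 90.4 | 89.8 → 89.8 | 86.0 → 86.0 | 2.5 |
| 2% | 90.6 → 90.9 | 90.0 → 90.4 | 86.2 → 86.7 | 2.4 |
| 5% | 91.0 → 91.8 | 90.4 → 91.2 | 86.6 → 87.7 | 2.2 |
| 10% | 91.5 → 93.1 | 91.0 → 92.6 | 87.2 → 89.3 | 1.9 |

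For the unadjusted GMC analysis to match the adjusted one, it would need about 0, 9, 23 and 47 more infants per arm.

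**Step 3. Loosen the balance.** SAP 5 sizes the trial "considering that 25% of the participants will not be evaluable for the analysis of the primary endpoint". If that quarter is lost at random after balanced allocation, replace √(1 − R) in the two unadjusted formulas by √(1 − 0.75R).
- Unadjusted error: 2.5, 2.4, 2.3, 2.1%.
- Unadjusted GMC power: 89.8, 90.0, 90.2, 90.7%.
- Largest single gain: ≥90 U/mL at R = 10%, where √(1 − 0.075) = 0.962. Unadjusted power is Φ((3.039 − 1.96)/0.962) = 86.9%, against 89.3% adjusted, a gain of 2.4 points.

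**Step 4. Simulate** (10 equal centres assumed, 1000 per arm, 25% random loss; R = 0, 2, 5, 10%).
- GMC, 20,000 trials per setting: power 89.6, 90.1, 90.6, 90.5% unadjusted against 89.6, 90.4, 91.5, 92.4% adjusted. One-sided error is 2.4, 2.4, 2.2, 2.1% against 2.4, 2.5, 2.4, 2.5%.
- Seroconversion, 60,000 trials: power 90.5, 90.3, 90.9, 91.7% unstratified against 90.5, 90.7, 91.7, 93.1% stratified.

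**Step 5. Effect on the hierarchy,** by the SAP's own method of summing type II errors (score-test variance for the two proportions, exact balance). For all three objectives the bound moves from 68.2 to 70.8% at R = 5% and from 70.0 to 75.2% at R = 10%. For the two primaries it moves from 81.4 to 83.0% and from 82.6 to 85.7%.

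**The case against.** The strongest reply is that nothing is broken. Protocol, SAP and power calculation all leave centre out consistently, the stated power is met, and a slightly wide interval makes a false non-inferiority claim less likely. All of that stands, and it is why this is an improvement rather than a correction.

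Further points:
- **The gain rests on an assumed R.** This stands. At 2% the gain is only about 0.3 to 0.5 points, and gains near 2 points need the top of the range.
- **Balance will not be exact.** SAP 6.1.3 allows forced and manual randomization, and per-protocol exclusions may cluster by centre. This stands as a limit on the figures. Random loss has been allowed for and does not remove the gain; clustered loss has not been modelled.
- **Adjustment can cost something.** In simulations of the two rate endpoints with no centre effect, the cost was up to 0.1 point with 10 to 20 equal centres and 0.2 with 40. That is too small to decide the matter, but it is a reason for a pooling rule.
- **The GMC method is unnamed, so centre cannot be shown to be left out.** Correct. The point is only that centre is not stated to be used, and naming a model settles both questions.
- **Site tables are planned.** They will show differences between centres, but they leave the confirmatory intervals unchanged.

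**Conclusion.** The point holds as an inexpensive improvement. Allocation is balanced on centre, and no confirmatory interval is stated to use it. The gain on a single objective runs from zero, if centres respond alike, to about 2.4 points, if centre explains 10% of the variance and a quarter of infants are lost at random. The unadjusted intervals are valid and conservative, and the stated power is not wrong.

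The size depends on the assumed R and on balance being near exact apart from random loss. The simulations also assume equal centres. The documents support no narrower range.

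**What to change.** Before unblinding, amend SAP 4.2.2 and 4.3.2:
- **GMC ratio:** estimate it with its 95% CI from a linear model on log10 concentration with group and centre.
- **Both rate differences:** use a centre-stratified Miettinen-Nurminen interval and state the weights (Mantel-Haenszel type).
- **Small centres:** fix a pooling rule in advance.
- **Sensitivity:** keep the unadjusted intervals as a sensitivity analysis.
- **Record:** update SAP 4.8, which now says "There were no changes or deviations to the originally planned statistical analysis specified in the protocol".

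If the sponsor prefers unadjusted intervals, the SAP should say so with a reason, and should still name the GMC method.

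The cost is SAP wording, standard code and the pooling rule. No extra data or infants are needed.

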5. STUDY POPULATION

5.1. Inclusion criteria for enrolment

Adherence to these criteria as specified in the protocol is essential. Inclusion criteria deviations are not allowed because they can jeopardize the scientific integrity or regulatory acceptability of the study or participant safety.

All participants must satisfy ALL of the following criteria at study entry:

- Participants' parent(s)/ LAR(s), who, in the opinion of the investigator, can and will comply with the requirements of the protocol (e.g., completion of the diary cards, return for follow-up visits).
- Written or witnessed/thumb printed informed consent obtained from the parent(s)/LAR(s) of the participant prior to performance of any study specific procedure.
- A male or female with Chinese origin, between, and including, 6 and 16 weeks (42-112 days) of age at the time of the first study intervention administration.
- Healthy participants as established by medical history and clinical examination before entering into the study.
- Born after a gestation period of 36 to 42 weeks inclusive.

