8.2.1. Procedures prior to study intervention administration

8.2.1.1. Collection of demographic data

Record demographic data such as date of birth including gestational age, sex, and race in the participants' eCRF.

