#### 6.1.2. Demographic and Baseline Characteristics

The demography and baseline characteristic summaries will be provided for both ES and PPS.

The median, mean, range and standard deviation of age (in weeks) for each dose of *Rotarix* and for gestational age (in weeks) will be computed by group. Median, mean and standard deviation of height in centimeter and weight in kilogram at Visit 1 will be computed by group. The study sites, geographical ancestry and sex composition will be presented by group.

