#### 6.2.5. Age at vaccination in weeks

Age at vaccination will be displayed in weeks. It will be calculated as the number of complete weeks between the date of birth (DOB) and the date of vaccination. For example:

DOB = 10JUN2019, Date of vaccination = 28JUL2019 -> Age = 6 weeks

DOB = 10JUN2019, Date of vaccination = 29JUL2019 -> Age = 7 weeks

Incomplete birthdate will follow the general imputation for incomplete date (refer to Section 6.2.3).

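### The GMC-ratio interval is valid but appears unadjusted; age at Dose 1, already derivable, could be pre-specified as a covariate for a small and uncertain gain in precision

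*SAP*

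**What the plan says.** SAP 4.2.2 names the Miettinen and Nurminen method for the seroconversion difference. For the GMC ratio it says only that "The 95% CI for the ratio of anti-RV IgA Ab GMCs at Visit 3 between" the PCV-free and current vaccines will be computed. Protocol 9.4.3.2 is equally brief.

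Two other places suggest that no covariate is meant. SAP 4.1.1 defines the GMC directly: "The GMC calculations will be performed by taking the anti-log of the mean of the log concentration transformations". SAP 5.1.2 sizes the comparison by a "one-sided non-inferiority test for 2 independent means, under the alternative of equal variance".

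On age, Protocol 5.1 admits infants between "6 and 16 weeks (42-112 days) of age at the time of the first study intervention administration". Protocol 8.2.1.1 has the site "Record demographic data such as date of birth including gestational age, sex, and race in the participants' eCRF". SAP 6.2.5 derives age at vaccination: "It will be calculated as the number of complete weeks between the date of birth (DOB) and the date of vaccination". The only planned use of it is the summary in SAP 6.1.2: "The median, mean, range and standard deviation of age (in weeks) for each dose of" vaccine, by group. The supplementary immunogenicity breakdowns do not involve age: "Within groups assessment for the PPS will be repeated by sex and study sites" (SAP 4.2.3). Protocol 6.3.3 minimizes on centre and the study as a whole, so balance of age between arms is left to chance.

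**The concern.** A continuous baseline variable that can be derived from data already collected is left out of a confirmatory comparison of means. If age at Dose 1 explains some of the variation in log10 IgA, a pre-specified adjustment narrows the interval for the ratio and corrects the estimate for any chance difference in age between arms. If it explains none, the cost is one degree of freedom out of 1,498.

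The usual first choice of covariate, the pre-vaccination titre, offers little or nothing here, because everyone in the Per-Protocol Set must be below 20 U/mL at baseline (SAP Section 3). Adjustment for centre is a separate question and is not argued here.

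The GMC ratio is the second step of a fixed hierarchy (SAP 2.1). If it fails, the 90 U/mL objective cannot be claimed either.

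**Working it through.** **Inputs.** From SAP 5.1.2 (Table 4): SD 0.797 on the log10 scale, 750 evaluable infants per arm, true ratio 0.91 or 1, limit 0.67, one-sided alpha 0.025, stated power 90.7% and 99.0%. Assumed: R², the share of within-group variance of log10 IgA that age at Dose 1 explains. The documents do not give it, so a range is shown.

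**Step 1: reproduce the plan's figure.**
- SE = 0.797 × √(2/750) = 0.04116.
- Distance from the limit at true ratio 0.91: log10(0.91) − log10(0.67) = 0.1330.
- Noncentrality = 0.1330 / 0.04116 = 3.231. With 1,498 degrees of freedom, power is 89.8%, against 90.7% stated.
- At true ratio 1 the distance is 0.1739, the noncentrality 4.226 and the power 98.8%, against 99.0% stated.
- With the limit taken as 2/3 instead of 0.67, the results are 90.7% and 99.0%. The small gap is consistent with rounding of the limit and is not pursued.

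**Step 2: add age.** The residual SD becomes 0.797 × √(1 − R²). The log-scale interval narrows by 1 − √(1 − R²), and the equivalent unadjusted size is 750 / (1 − R²). At true ratio 0.91 and limit 0.67:

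| R² | Power | Interval narrower by | Equivalent n per arm |
|---|---|---|---|
| 0 | 89.8% | 0 | 750 |
| 1% | 90.1% | 0.5% | 758 |
| 2% | 90.4% | 1.0% | 765 |
| 5% | 91.2% | 2.5% | 789 |
| 10% | 92.6% | 5.1% | 833 |

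At true ratio 1 there is little left to gain: 98.8% unadjusted, 99.1% at R² = 5%.

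**Step 3: cost if age is not prognostic.** Going from 1,498 to 1,497 degrees of freedom leaves power at 89.8%.

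**Step 4: effect on a reported result.** If the observed ratio is 0.91, the lower limit is 10^(log10 0.91 − 1.9615 × 0.04116) = 0.756 unadjusted. At R² = 5% the SE is 0.04011 and the limit is 0.759. SAP 6.2.10 shows GMC ratios to two decimals, so both appear as 0.76.

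**Step 5: chance imbalance.** If R² = 5%, an age imbalance at the unfavourable 2.5% point shifts the unadjusted log10 ratio by 1.96 × √0.05 × 0.797 × √(2/750) = 0.0180, a factor of 10^(−0.0180) = 0.96. The unadjusted standard error already allows for this variation, so it restates the gain in Step 2 and does not add to it.

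**The case against.** The strongest reply is that nothing is wrong. Comparing two means on the log scale agrees with the SAP's definition of a GMC and with its power calculation, and randomization makes the interval valid. That stands in full. A reader might infer that the unadjusted ratio is biased or the analysis deficient; the documents support neither.

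Second, nothing in the documents says that age predicts IgA. Sex, gestational age and weight are also recorded, and the 42 to 112 days are an eligibility window, not the ages that will be enrolled. This also stands. A reader might take the wide window as evidence that age is prognostic, but it shows only that age may vary. The case for age is that it is available and cheap to use, not that it is known to work.

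Third, the gain is small. The rise from R² = 0 to 2% (0.6 points) is less than the 0.9-point gap between the stated 90.7% and the recomputed 89.8%. In addition, values below the assay cut-off are set to half of it (SAP 4.1.1). If that cut-off is the 20 U/mL seropositivity threshold, about 30% of values would sit at one point at the expected seroconversion of 67.8% to 70%, which may limit the R² attainable. Dependence of the secondary objective on this step adds little, since that chain also runs through two proportion endpoints that the change does not touch.

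Fourth, the change is not entirely free. A complete birth date cannot be assumed for every infant: SAP 6.2.5 refers incomplete ones to the general imputation rule in 6.2.3 (day 15, or 30 June), which can be far out for an infant 6 to 16 weeks old. Age in days is a new derivation, because the SAP uses completed weeks. The adjusted ratio will also differ slightly from the ratio of the two reported GMCs. These points shape the fix but do not remove the reason for it.

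**Conclusion.** The point holds as an optional, low-priority refinement. That the interval is unadjusted is inferred from the SAP's silence on a model, its GMC definition and its two-sample power calculation; it is not stated outright.

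At true ratio 0.91 the gain is 0.3 points of power at R² = 1%, 1.4 at 5% and 2.8 at 10%, and zero if age is not prognostic. These figures rest on the plan's SD of 0.797, 750 evaluable infants per arm, a linear age effect and an R² that the documents do not supply. The recomputed 89.8% should not be read as a shortfall against the stated 90.7%, since a limit of 2/3 recovers the stated figure.

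**What to change.** Before unblinding, state in SAP 4.2.2 that the GMC ratio and its 95% CI come from a linear model of log10 concentration on vaccine group and continuous age at Dose 1, back-transformed, with the 0.67 limit unchanged. In the same edit:

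- define age in days from date of birth to Dose 1, since SAP 6.2.5 gives completed weeks only;
- say how incomplete birth dates are handled in the model, rather than letting the general rule in 6.2.3 apply by default;
- use the same model if the analysis is repeated on the Exposed Set (SAP 4.2.3);
- report the unadjusted ratio as supportive;
- record the change in SAP 4.8, which now declares none.

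The cost is a short SAP revision, one derivation and one degree of freedom. Sample size and data collection do not change. Two ratios will appear in the report, and a footnote should explain why the adjusted one differs slightly from the ratio of the tabulated GMCs.
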